9.4. Randomisation

Randomisation of treatment order will be performed using "Sealed Envelope" (http://www.sealedenvelope.com/). As this is a cross-over study randomisation will be simple and not minimised or stratified.

9.5. Blinding and code-breaking

This is a single blinded trial so the investigator will be aware of the blinding and can unblind the participant if required. The researcher will not be blinded as they will need to set-up and supply either the sham-CPAP or CPAP. Out of hours unblinding will not be required due to the low risk of the intervention of CPAP withdrawal. Patients are sometimes aware that the sub-therapeutic CPAP is not as effective as their usual, so are not truly blind. However, the measurements in this study are all objective rather than subjective. This has been the case in previous CPAP withdrawal studies.

9.6. Description of study intervention(s), comparators and study procedures (clinical)

CPAP therapy/CPAP withdrawal

All subjects will have been using CPAP for more than three months and will be familiar with it. They will continue to use their usual CPAP mask for the duration of the study but will swap to a ResMed S9 or S10 autoCPAP machine which is essentially no different, but is able to record nightly compliance, mask leak and residual apnoeas accurately. Sub-therapeutic CPAP will be delivered as in all our previous studies (41, 67, 69-71). The CPAP is rendered sub-therapeutic by first setting it to the lowest pressure possible (4cms H_2O), and the pressure lowered still further (to 1cm H_2O) using extra blow-off holes in the mask tubing at the patient end (which also ensures full blow off of exhaled CO_2). The machine is restrained from trying to compensate for this extra leak with a 5mm restriction introduced at the machine end of the tubing.

9.6.1. Description of study procedure(s)

Bloods

Participants will have blood samples taken at the screening visits and visits 1, 2, 3 and 4. These will be performed using sterile technique using standard venepuncture technique. Samples will be analysed as detailed below.

Continuous glucose monitoring

At visits 1 and 3 participants will have continuous glucose monitoring supplied and established (G6 sensor and transmitter, Dexcom). They consist of a sensor with of a small needle, usually the width of a small hair attached to a patch that is inserted under the skin on the upper arm or the abdomen. The researcher will fit the participant with the sensor using a one-touch applicator to insert a small sensor just beneath the skin, either sited on the upper arm or the abdomen (participant's preference). This will be performed as per the manufacturers standard operating procedures. The device will then continuously record glucose levels. This device will then be worn for seven days until it is removed at visit 2. The device is water resistant meaning that participants will be able to shower but not swim or bathe during the trial.

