A Cochrane review showed that the use of CGM can improve HbA_{1c} levels in patients with type 1 diabetes mellitus (T1DM) but leads to increased hypoglycaemia when used to direct insulin pump therapy, compared to standard glucose monitoring (48). This has led to NICE recommending their use for a limited number of patients with T1DM, including those with hypoglycaemic difficulties and those with an elevated HbA_{1c} despite frequent monitoring (49). CGM does have drawbacks, particularly with accuracy of their recordings. CGMs do not measure blood or plasma glucose levels, instead they measure interstitial fluid glucose levels. Whilst interstitial glucose levels are closely related to blood and plasma glucose levels they are probably less accurate than standard blood glucose monitoring and gold-standard laboratory glucose measurements, with mean absolute relative differences of between 10-12% for both "flash" and "true" CGM devices (50-53). The differences in measurement however, have little impact on clinical outcome with 85-87% of results leading to the same clinical management and 99% of results leading to the same clinical outcome with CGM, compared to standard glucose monitoring (50, 51). There is a lag-time of 4.5 ± 4.8 minutes for changes in blood glucose levels to be reflected in changes in interstitial CGM readings. Despite, CGM being slightly less accurate than blood glucose monitoring the ability to continuously monitor glucose levels overnight without admission to hospital means this is an ideal way to monitor the effects of OSA on glycaemic control. In addition, 98.6% of patients found the pain of CGM as acceptable or better than standard glucose monitoring (50). The device we intend to use - the Dexcom G6 - has a 10 day sensor life, with 87% of monitors surviving to 10 days (53).

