Others have used similar short-term CPAP withdrawal protocols to demonstrate changes in glycaemic control both in patients without diabetes, and patients with T2DM not on insulin (74). They conducted randomised cross-over trial of three nights CPAP withdrawal versus continued CPAP. They conducted a full in-lab polysomnography (PSG) on the 3rd night of CPAP withdrawal and compared this to an on CPAP PSG night. They looked at blood glucose levels drawn from a venous catheter at regular intervals throughout the night. They found that CPAP withdrawal increased overnight glucose levels by 5.57 mg/dl (95% confidence interval or CI 0.59, 10.55, p=0.028). In a subgroup analysis they showed that this effect was only in the diabetic patients, with CPAP withdrawal increasing blood glucose levels by 17.2mg/dl in diabetic participants (95% CI 0.13, 34.6, p=0.04). It is worth noting that this was not a pre-planned subgroup analysis and that only 7 of 31 patients were diabetic. Other hospital based studies have explored the effect of CPAP on blood glucose control, with one randomised control trial enrolling patients with OSA and "prediabetes" and admitting them to hospital for two-weeks (75). Patients were randomised to either 8 hours per night of CPAP or oral placebo on a 2:1 basis and had attended PSG every night with CPAP adherence ensured by continual supervision. They then assessed the glucose response curve following an oral glucose tolerance test (OGTT) in the morning. They showed small improvements in the glucose response curve and in insulin sensitivity.

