9.7. Baseline Assessments

Participants will attend for Visit 1 at least 14 days and no more than 12 weeks from their screening visit. Eligibility criteria will be checked including screening oximetry and HbA1c levels.

Participants will need to have fasted for 8 hours prior to this visit.

First, participants will have their office blood pressure and heart rate recorded in triplicate following at least 5 minutes of rest in a seated position from their left arm. At least one minute will be allowed between each blood pressure measurement.

Second, participants will have blood tests taken, totalling a maximum of 35ml (around two tablespoonsful). These will be sent for glucose levels, insulin levels, full blood count, urea, creatinine and electrolytes, lipid profile and for plasma/serum storage for markers of cardiovascular disease.

Participants will be requested to complete an Epworth sleepiness score, an eight-point questionnaire.

At Visit 1 the researcher will supply the participant with a continuous glucose monitor (Dexcom G6®) sensor and transmitter as described in the procedures section. Participants will have this process repeated at Visit 3 after crossing over.

Clinical Research Protocol Template version 15.0

CONFIDENTIAL

At Visit 1 participants will be supplied with pulse oximetry (Minolta 300i). Every night, oxygen saturation measurements (and pulse rate rises) will be performed at home using this simple overnight pulse oximeter. Participants will have this process repeated at Visit 3 after crossing over.

Data from participants' CPAP machine will be downloaded for an average use of CPAP over all days in the last 14 days prior to the visit. This will not be assessed as an eligibility criterion as this will have already been assessed at the screening visit (see section 9.3).

Eligibility criteria will be checked prior to randomisation. Participants will then be supplied with a new CPAP machine, either therapeutic or sham. The participant's own CPAP machine will be collected and securely stored until Visit 2.

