9.8. Subsequent Visits

The assessments at these visits will be identical to the baseline assessments at Visit 1 described in Section 9.6 aside from the following assessments.

Participants will attend Visit 2 seven days after Visit 1, and Visit 4 seven days after Visit 3. Following Visit 2 participants will return to using their own CPAP machine for at least 14 days prior to returning for Visit 3.

CGM and oximetry data will be downloaded at visits 2 and 4. At Visit 3 participants will be supplied with a continuous glucose monitor (Dexcom G6®) as described in Section 9.6.

Data from participants CPAP machine will be downloaded for an average use of CPAP over all intervention days at Visits 2 and 4. At visit 3 data from participants' CPAP machine will be downloaded for an average use of CPAP over all days in the last 14 days prior to visit. This will not be assessed as an eligibility criterion as this will have already been assessed at the screening visit.

At visits 2 and 4 participants will have their own CPAP machine returned and will be instructed to restart using this from the night following this visit. At Visit 3 participants will then be supplied with a new CPAP machine, either therapeutic or sham. The participant's own CPAP machine will be collected and securely stored until Visit 4.

At the end of study visit 4 the participants will be asked to return all study equipment and participants' involvement in the study will end.

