11.3. Sample Size Determination

The sample size calculation is based on the difference in mean overnight glucose levels. This was chosen as the primary outcome as paired pilot data exists for this outcome, unlike other CGM metrics like MAGE or NMAGE which are instead included as secondary outcomes. The sample size calculation is based on pilot data from Chopra *et al.* (74), who looked at the difference in overnight blood glucose levels measured in a hospital setting over three nights of CPAP withdrawal in patients with T2DM and OSA. They found a between group difference of 17.2 19.0 mg/dl. Based on this, in order not to miss a between-group difference in overnight glucose levels of 17.2mg/dl between CPAP withdrawal and continued CPAP with a two-sided alpha of 0.05 and a beta of 0.8 would require 22 participants in a crossover study. An alternative would be to base our power calculation on data from Mokhlesi *et al.* (76), who looked at the difference in 24 hour blood glucose levels measured in hospital over 7 days in patients treated with CPAP with T2DM

and OSA. They found a 13.5 13.5 mg/dl improvement in 24 blood glucose levels with CPAP therapy. Based on this, in order not to miss a between group difference in 24-hour glucose levels of 13.5 mg/dl between CPAP withdrawal and continued CPAP with a two-sided alpha of 0.05 and a beta of 0.8 would require 18 participants in a crossover study.

Taking the more conservative estimate of 22 participants, and allowing for only 87% of CGM monitoring sensors surviving the 10 day follow-up period (53) from application, gives 25 patients. In previous parallel CPAP withdrawal trials drop-out rates following randomisation has been 1% (65). Therefore, allowing for a more conservative drop-out rate of 10% we will aim to randomise 30 patients. However, when 22 patients have completed the trial per protocol with sufficient CGM data recruitment will be stopped.

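### The paired contrast compares two different glucose sensors, with insertion site free to differ between periods, and the sample size makes no allowance for the variance this adds

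*Protocol*

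**What the plan says.** Protocol 9.6.1: "At visits 1 and 3 participants will have continuous glucose monitoring supplied and established". Section 9.7 confirms it for the second period: "Participants will have this process repeated at Visit 3 after crossing over". Section 5 says that the device "has a 10 day sensor life, with 87% of monitors surviving to 10 days", and 9.8 sets the gap between periods: "Following Visit 2 participants will return to using their own CPAP machine for at least 14 days prior to returning for Visit 3". One sensor therefore cannot serve both arms.

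On placement, 9.6.1 has the sensor inserted "just beneath the skin, either sited on the upper arm or the abdomen", as the participant prefers. No passage ties the second site to the first.

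On accuracy, section 5 describes CGM devices "with mean absolute relative differences of between 10-12" percent from reference measurements. It does not split this error into a part that stays with a sensor and a part that varies between readings.

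On sample size, 11.3 relies on a hospital crossover study "who looked at the difference in overnight blood glucose levels measured in a hospital setting over three nights of CPAP withdrawal". Section 5 says how that study measured glucose: "They looked at blood glucose levels drawn from a venous catheter at regular intervals throughout the night". Section 11.3 then inflates for 87% sensor survival and 10% drop-out, and stops recruitment once 22 participants have completed with sufficient CGM data.

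A fasting laboratory glucose is taken at Visits 1 to 4 (procedures table in section 9; section 9.9.1). No passage compares it with the CGM trace or says whether the blood is drawn before the sensor is removed.

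**The concern.** A crossover removes whatever is constant within a person. An error that belongs to one sensor, or to one insertion site when the site changes, is not constant within a person here, because each arm has its own sensor. Averaging many readings a night over three nights does not reduce it either. It stays in the paired difference.

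The effect sought is of the same order as the device error. At an assumed overnight mean of 140 mg/dl, 17.2 mg/dl is 12% of the mean (17.2/140), against a stated error of 10-12%. The earlier study's whole-sample effect, 5.57 mg/dl, is 4% (5.57/140). Its SD came from venous sampling, which has no sensor-to-sensor component. What is at stake is precision: a wider interval and less power than 11.3 implies. Because recruitment stops at 22 completers, the target of 30 randomised gives no reserve against extra variance.

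**Working it through.** **Inputs from the protocol.** Effect 17.2 mg/dl and 19.0 read as an SD (11.3); two-sided alpha 0.05, 80% power, n = 22 (11.3); mean absolute relative difference (MARD) 10-12% (section 5); diabetic-subgroup interval 0.13 to 34.6 mg/dl in 7 participants (section 5).

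**Assumptions not in the protocol.** Overnight mean 140 mg/dl; normal errors centred on zero; 25-75% of the per-reading error variance persistent within a sensor.

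**1. Reproduce 22.** Paired t test, noncentral t.
- If 19.0 is a per-period SD, the SD of the difference is 19.0 × √2 = 26.9. This needs n = 22, with power 82%. The same reading gives 18 for the alternative inputs of 13.5 and 13.5, as stated in 11.3.
- If 19.0 is the SD of paired differences, n = 12 suffices, and 22 gives 98% power.

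Only the per-period reading reproduces the protocol's figures.

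**2. Which reading does the earlier study support?** The half-width of its interval is (34.6 − 0.13)/2 = 17.2. Dividing by t(0.975, 6 df) = 2.447 and multiplying by √7 gives an SD of paired differences of about 18.6. So 19.0 looks like an SD of differences, although that rests on seven people in a subgroup that was not pre-planned.

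**3. Add sensor error.** For normal errors the per-reading SD is MARD × √(π/2) × mean, that is 0.10 × 1.253 × 140 = 17.5 up to 0.12 × 1.253 × 140 = 21.1 mg/dl. With a persistent share p, the sensor SD is b = per-reading SD × √p. Two independent sensors give SD of the difference = √(base² + 2b²).

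| Case | b (mg/dl) | SD, base 19.0 | Power, n = 22 | SD, base 26.9 | Power, n = 22 |
|---|---|---|---|---|---|
| No sensor error | 0 | 19.0 | 98% | 26.9 | 82% |
| MARD 10%, p = 25% | 8.8 | 22.7 | 92% | 29.6 | 74% |
| MARD 11%, p = 50% | 13.6 | 27.1 | 81% | 33.1 | 64% |
| MARD 12%, p = 75% | 18.2 | 32.0 | 67% | 37.2 | 54% |

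Across the three sensor-error rows, n for 80% power is 16, 22 and 30 on base 19.0, and 26, 32 and 39 on base 26.9. On base 19.0, 22 participants absorb a sensor SD of up to about 14 mg/dl.

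**4. Sensitivity to the assumed mean.** Over means of 110 to 160 mg/dl, with the same MARD and p ranges, power at n = 22 runs from 95% to 59% (base 19.0) and from 77% to 49% (base 26.9).

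**5. Is the test still valid?** A simulation of 22 participants with no treatment effect, base SD 19 and sensor SD 14 gave a mean difference of about 0 and a type I error of 4.8%.

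**The case against.** A reader might infer that uncorrected sensor bias enters the treatment effect. The documents do not support that. Treatment order is randomised (9.4), so an offset unrelated to arm has mean zero in the contrast, and an offset common to all sensors cancels within person. The observed SD of differences already contains sensor variance, so the interval and test are honest. Nothing in the protocol links site choice or sensor behaviour to arm. This part of the objection stands in full.

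Separate sensors are unavoidable given sensor life and washout, so using them is not an error. That also stands.

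The size rests on assumed inputs. MARD mixes common bias, which cancels, with reading-to-reading noise, which averages out, so treating all of it as random overstates what can be sensor-specific. The lowest powers combine the top MARD, the top persistent share and the SD reading that the earlier study's interval does not support. This trial also averages three nights where that study compared single nights, which should reduce other noise and is not credited above. These points make the loss conditional but do not remove it: 11.3 neither mentions sensor error nor says which SD 19.0 is, so any spare power is accidental.

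Section 9.6.1 mentions preference once, and section 9.7 says only that the process is repeated. A change of site is possible, but the documents give no frequency for it and no arm-abdomen difference.

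A model using the laboratory values could be in the separate SAP, so its absence here is no fault. The insertion site and the order of blood draw and sensor removal are visit procedures, which a later SAP cannot recover.

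**Conclusion.** The point holds as one of precision. Two sensors per participant, with site free to differ, add variance to the paired primary contrast, and 11.3 allows for sensor survival but not for sensor accuracy. The estimate and its type I error are sound.

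Under the stated assumptions, power at 22 is 92-67% on the SD reading that the earlier study's interval supports, with the middle case still meeting the planned 80%. It is 74-54% on the reading that reproduces 22. The protocol gives neither the overnight mean nor the persistent share of device error, so no single figure can be defended. This is a low-cost improvement, best made before data collection.

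**What to change.** - **9.6.1:** require the same insertion site (arm or abdomen) in both periods for each participant.
- **9.8:** at Visits 2 and 4, take the fasting laboratory glucose before the sensor is removed and record the time of the draw. Report the CGM-minus-laboratory difference by arm as a sensor check. Any model adjusted for that difference should be a sensitivity analysis only.
- **11.3:** state that the inputs are venous and exclude sensor error, and say whether 19.0 is the SD of paired differences or a per-period SD. A short range of power that includes sensor error would follow from this.

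Cost: no new samples, visits or participants. Participants lose a free choice of site in the second period. One paired value per sensor, taken in the morning, is a noisy check on overnight error, which is why it should not enter the primary model.

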9.7. Baseline Assessments

Participants will attend for Visit 1 at least 14 days and no more than 12 weeks from their screening visit. Eligibility criteria will be checked including screening oximetry and HbA1c levels.

Participants will need to have fasted for 8 hours prior to this visit.

First, participants will have their office blood pressure and heart rate recorded in triplicate following at least 5 minutes of rest in a seated position from their left arm. At least one minute will be allowed between each blood pressure measurement.

Second, participants will have blood tests taken, totalling a maximum of 35ml (around two tablespoonsful). These will be sent for glucose levels, insulin levels, full blood count, urea, creatinine and electrolytes, lipid profile and for plasma/serum storage for markers of cardiovascular disease.

Participants will be requested to complete an Epworth sleepiness score, an eight-point questionnaire.

At Visit 1 the researcher will supply the participant with a continuous glucose monitor (Dexcom G6®) sensor and transmitter as described in the procedures section. Participants will have this process repeated at Visit 3 after crossing over.

Clinical Research Protocol Template version 15.0

CONFIDENTIAL

At Visit 1 participants will be supplied with pulse oximetry (Minolta 300i). Every night, oxygen saturation measurements (and pulse rate rises) will be performed at home using this simple overnight pulse oximeter. Participants will have this process repeated at Visit 3 after crossing over.

Data from participants' CPAP machine will be downloaded for an average use of CPAP over all days in the last 14 days prior to the visit. This will not be assessed as an eligibility criterion as this will have already been assessed at the screening visit (see section 9.3).

Eligibility criteria will be checked prior to randomisation. Participants will then be supplied with a new CPAP machine, either therapeutic or sham. The participant's own CPAP machine will be collected and securely stored until Visit 2.

9.8. Subsequent Visits

The assessments at these visits will be identical to the baseline assessments at Visit 1 described in Section 9.6 aside from the following assessments.

Participants will attend Visit 2 seven days after Visit 1, and Visit 4 seven days after Visit 3. Following Visit 2 participants will return to using their own CPAP machine for at least 14 days prior to returning for Visit 3.

CGM and oximetry data will be downloaded at visits 2 and 4. At Visit 3 participants will be supplied with a continuous glucose monitor (Dexcom G6®) as described in Section 9.6.

Data from participants CPAP machine will be downloaded for an average use of CPAP over all intervention days at Visits 2 and 4. At visit 3 data from participants' CPAP machine will be downloaded for an average use of CPAP over all days in the last 14 days prior to visit. This will not be assessed as an eligibility criterion as this will have already been assessed at the screening visit.

At visits 2 and 4 participants will have their own CPAP machine returned and will be instructed to restart using this from the night following this visit. At Visit 3 participants will then be supplied with a new CPAP machine, either therapeutic or sham. The participant's own CPAP machine will be collected and securely stored until Visit 4.

At the end of study visit 4 the participants will be asked to return all study equipment and participants' involvement in the study will end.

9.8.1. COVID-19 alterations

All visits, including the screening visit and visits 1-4, require face-to-face appointments given the requirement for blood tests at all time points. Face-to-face visits will be conducted in line with the latest government advice and the latest hospital infection control procedures including but not limited to the use of hand hygiene, face masks, and personal protective equipment. Should face-to-face hospital visits not be possible, home face-to-face visits will be considered providing this is in line with the latest government advice.

